9.2. Intent-to-Treat Infected (ITT-I) Population

The intent-to-treat infected (ITT-I) population will consist of all randomised participants who received challenge virus and at least 1 dose of IMP, and meet the criterion for RSV infection. Participants will be analysed in the treatment group they were randomised to.

As per Section 10.7.2 in the protocol, a laboratory-confirmed RSV infection requires one or both of the following definitions to be met:

- At least 2 positive detections by viral load qRT-PCR assay specific for the challenge virus, reported on 2 consecutive days;
- One positive detection by viral load qRT-PCR assay, specific for the challenge virus, in which an aliquot of the same sample has also tested positive in a viral culture assay appropriate for detecting the challenge virus.

For qRT-PCR and the viral culture assay a positive detection is any positive numeric or “detected” value.

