10.7. Statistical Analysis

All efficacy analyses will be based on the ITT-I population as the primary analysis. Where the populations differ to ITT-I population by 1 participant within a treatment group, the primary and selected secondary analyses will be repeated for the ITT-A, ITT-B, ITT and PP populations. This will be reviewed and documented at the BDRM.

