Date and time of first confirmed negative test after peak viral culture measurement – Date and time of first IMP administration.

A negative test is defined as a 'Not Detected' result in the viral culture test, with the date and time of the first negative test being utilised in the calculations. The peak viral culture measurement is defined as the highest viral load value obtained by a participant after their first administration of IMP. Participants who did not have a confirmed undetectable assessment after first administration of IMP are censored at their last detectable assessment after their peak viral culture measurement. Participants who stay undetectable during quarantine will be excluded from this analysis.

The time to the confirmed negative test will be summarised descriptively by treatment group. Kaplan Meier curves will be produced for each treatment group, overlayed on one plot. A supporting table will include the median, 25th and 75th percentiles for each group and will be accompanied by a log rank test to compare between RV299 and placebo with the corresponding p-value presented.

[Kaplan-Meier plot: y-axis = cumulative proportion of participants without a negative test, x-axis = day relative to initial administration of IMP, one line for each treatment overlayed on the same plot].

Time to Confirmed Negative Test by Viral Culture Measurements in Nasal Samples Starting from Peak Viral Culture after Initial Administration of IMP to First Confirmed Undetectable Assessment after Peak Measure

The time from the peak viral culture measurement after administration of IMP to the first confirmed negative viral culture measurement will be calculated in days as:

Date of and time first confirmed negative test – Date and time of first IMP administration.

A negative test is defined as two consecutive 'Not Detected' results in the viral culture test, with the date and time of the first negative test being utilised in the calculations. The peak viral culture measurement is defined as the highest viral load value obtained by a participant after their first administration of IMP. Participants who did not have a confirmed undetectable assessment after their peak viral culture measurement after first administration of IMP are censored at their last detectable assessment. Participants who stay undetectable during quarantine will be excluded from this analysis.

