[Line graph: y-axis = mean of total symptoms score, x-axis = day relative to dosing (the axis will be negative to include days prior to IMP administration), one line for each treatment group on same plot].

A boxplot will also be presented by day (relative to first dose of IMP) and assessment, plotting the median and mean qRT-PCT values for each treatment group, with the corresponding summary statistics.

[Box plot: y-axis = mean of qRT-PCR (\log_{10} copies/mL), x-axis = day relative to dosing, one box-and-whisker for each day, with each treatment panelled with RV299 at the top and placebo below].

Note: For multiple assessments taken within each day, so as to be able to plot mean values across participants (within a treatment group) by day, the actual collection time point (which may differ across participants) will not be used. Rather all first, second and third assessments will have mean values separately calculated and plotted as three means within each day. These three means will be shown equally spaced along the x-axis within the graph.

Area under the Curve over Time of Total Clinical Symptoms Change from Baseline (TSS-AUC-CFB) as Measured from 10 Symptoms within the Graded Symptom Scoring System Collected 3 Times Daily Starting at Initial Administration of IMP up to Planned Discharge from Quarantine

The change from baseline will be calculated for each assessment following administration of IMP and an AUC calculated using these scores will be analysed in the same manner as described above

(including sensitivity analyses 1 and 2), where the baseline assessment is the assessment nearest to the time of the first administration of IMP (can be prior to or after dosing, depending on whether dosed in the morning or evening).

Peak Symptoms Diary Card Score: Peak Total Clinical Symptoms (TSS) as Measured from 10 Symptoms within the Graded Symptom Scoring System Collected 3 Times Daily Starting from Initial Administration of IMP up to Planned Discharge from Quarantine

Using the scheduled protocol assessments from the assessment at the time of the first dose of IMP to Day 12 (Quarantine discharge), the highest total symptom score (defined as the sum of all 10 individual composite symptoms) will be summarised by treatment group and modelled in the same way as the main analysis of the primary endpoint.

Participants who do not record any symptoms will be assigned a peak of 0.

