Peak Daily Symptom Score: Individual Maximum Daily Sum of Symptom Score from Initial Administration of IMP up to Planned Discharge from Quarantine

The highest total symptom score recorded on each day, across the three assessments, for each participant will be summarised descriptively by treatment group and assessment day.

Time to Symptom Resolution as Measured from 10 Symptoms within the Graded Daily Symptom Scoring System Starting at Initial Administration of IMP to 24-hours Symptom Free

Symptom resolution is defined as a participant scoring 0 for the total symptom score for a 24 hour period (e.g a minimum of three consecutive symptom diary cards, each with a score of 0) after their peak symptom score.

The time from the assessment at the time of the first administration of IMP until symptom resolution will be calculated in days as:

Date and time of symptom resolution – Date and time of assessment at IMP administration.

The time to symptom resolution will be summarised by treatment group using descriptive summaries.

If the peak symptom score occurs on more than one day then the first occurrence will be selected. Participants who do not record 24 hours symptom free after their highest total symptom score during the quarantine period will be censored at their last assessment and participants who record no symptoms during quarantine will be excluded from this analysis.

Time to Symptom Resolution as Measured from 10 Symptoms within the Graded Daily Symptom Scoring System Starting at Peak Symptoms after Initial Administration of IMP to 24-hours Symptom Free

The time from the highest total symptom score following administration of IMP until symptom resolution will be calculated in days as:

Date and time of symptom resolution – Date and time of highest total symptom score.

The time to symptom resolution after the peak symptom score will be summarised by treatment group using descriptive summaries.

If the peak symptom score occurs on more than one day then the first occurrence will be selected. Participants who do not record 24 hours symptom free after their highest total symptom score during the quarantine period will be censored at their last assessment and participants who record no symptoms during quarantine will be excluded from this analysis.

Time to Peak as Measured from 10 Symptoms within the Graded Daily Symptom Scoring System Starting from Initial Administration of IMP to the Time of Peak Daily Symptom Score

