The time from the assessment at the time of the first dose of IMP (can be prior to or after dosing, depending on whether dosed in the morning or evening) until the highest total symptom score will be calculated in days as:

Date and time of highest total symptom score – Date of and time of assessment at IMP administration.

The time to peak daily symptom score will be summarised by treatment group using descriptive summaries.

If the peak symptom score occurs on more than one day then the first occurrence will be selected. Participants who record no symptoms during quarantine will be censored at their last assessment.

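### Dropping never-culture-positive and symptom-free ITT-I participants from time to culture-negative and time to symptom resolution conditions on a post-randomisation outcome, and can hide an effect if RV299 prevents culturable virus or symptoms

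*SAP*

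**What the plan says.** SAP 10.7 sets the analysis population: "All efficacy analyses will be based on the ITT-I population as the primary analysis". SAP 9.2 lets a participant qualify as infected on PCR alone: "At least 2 positive detections by viral load qRT-PCR assay specific for the challenge virus, reported on 2 consecutive days". A positive culture is needed only for the alternative criterion.

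Within that population, participants without culturable virus or symptoms are handled in three ways:

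- **Excluded.** Both culture time-to-negative endpoints (SAP 10.7.2.3): "Participants who stay undetectable during quarantine will be excluded from this analysis". Both time-to-resolution endpoints (SAP 10.7.2.4): "participants who record no symptoms during quarantine will be excluded from this analysis".
- **Kept at the best value.** Peak symptom score: "Participants who do not record any symptoms will be assigned a peak of 0". Peak culture load likewise takes the Not Detected value, which SAP Appendix 15.1 sets to 0.
- **Censored.** Time to peak symptoms: "Participants who record no symptoms during quarantine will be censored at their last assessment".

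The culture endpoints carry a "log rank test to compare between RV299 and placebo with the corresponding p-value presented". The protocol planned no inference for them; SAP Section 11 adds the test as needed to support the study outcome. Symptom resolution has no test: "The time to symptom resolution will be summarised by treatment group using descriptive summaries".

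The exclusions do not appear in the protocol's endpoint definitions (Section 3) or among the changes in SAP Section 11. No planned table gives the never-culture-positive or symptom-free share by arm, and no planned analysis keeps these participants in these endpoints.

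**The concern.** Dosing starts about 12 hours after the qicPCR-positive nasal wash, from the evening of Day 2 at the earliest (SAP 6.1). That can be before virus is culturable or symptoms begin. Protocol Section 2.2 describes N-protein inhibition as stopping the formation of new virus particles. An infected participant who never becomes culture-positive, or never has symptoms, may therefore be showing a treatment effect.

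Removing such participants conditions the comparison on something that happens after randomisation. If RV299 makes it more common, more of its good outcomes leave the analysis than placebo's. The log-rank test then compares only those who shed culturable virus in each arm. A drug that acts partly by prevention would look weaker than it is, and nothing planned beside the table would show why.

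**Working it through.** **No figure to reproduce.** The documents state no power, effect size or variability for these endpoints, and the visible text gives only the planned 40 per arm.

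**Inputs from the documents.** Planned size is 40 per arm (SAP 6.1). The infection rate is 65% to 85% (Protocol 2.3), giving 40 × 0.65 = 26 to 40 × 0.85 = 34 ITT-I participants per arm; 40 × 0.75 = 30 lies between. Tests are two-sided at 5% (SAP 10.1.4). Washes are taken every 12 hours. There are seven possible first-dose slots, from Day 2 evening to Day 5 evening, so follow-up to the Day 12 morning is 6.5 to 9.5 days.

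**Assumptions, not in the documents.** These are the never-culture-positive shares and the clearance times in the rest. Both are varied below.

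**Model 1.** 30 per arm; Weibull clearance times (shape 2, placebo median about 4 days) rounded up to 12-hour samples; 2,000 trials per scenario. Never-positive participants are either excluded or given an event at 0.5 day.

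| Never positive, placebo / RV299 | Clearance in the rest on RV299 | Rejection, excluded | Rejection, all kept |
|---|---|---|---|
| 20% / 35% | same | 5-6% | 11% |
| 20% / 45% | same | 5-6% | 21-24% |
| 20% / 50% | same | 5-6% | 29-30% |
| 20% / 45% | 20% shorter | 26-27% | 61-63% |
| 20% / 20% | 20% shorter | 31% | 25-26% |
| 20% / 20% | 35% shorter | 81% | 68% |
| 40% / 40% | 35% shorter | 67% | 47% |

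Ranges are across repeat runs. The medians can be checked by hand. With everyone kept, S_all(t) = (1 − p) × S_pos(t) after the first post-dose sample, so the median solves S_pos(t) = 0.5 / (1 − p). With S_pos(t) = 0.5^((t/4)²):

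- Placebo, p = 0.20: S_pos = 0.625, t = 4 × √(0.470/0.693) = 3.3, or 3.5 days on the 12-hour grid.
- RV299, p = 0.45: S_pos = 0.909, t = 4 × √(0.095/0.693) = 1.5 days.

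The simulated mean medians are 3.5 and 1.7 days. With the exclusion they are 4.25 and 4.28 days, so the difference disappears. On average 30 × 0.20 = 6 placebo and 30 × 0.45 = 13.5 RV299 participants are dropped.

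**Model 2.** 26 or 34 per arm; exponential clearance; 8 days of follow-up; 1,500 trials per scenario. Never-positive participants are excluded or counted at time 0, and the difference in mean time to negative is restricted to 6.5 days.

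- 10% / 30%, median 4 days in both arms: difference 0.0 days excluded and 0.8 kept; rejection 5-7% and 15-19%. By hand, the restricted mean among positives is about 4.1 days, and (0.30 − 0.10) × 4.1 = 0.8.
- 10% / 50%, same medians: 0.0 and 1.6 days; rejection about 6% and 45-55%.
- Equal shares (10% to 30%), medians 4 versus 2.5 days: 0.8 days excluded and 0.6 to 0.8 kept; rejection 23-38% and 16-34%.
- Equal shares (10% or 20%), no drug effect: about 4-6% either way.

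The two models agree. Exclusion attenuates the effect when RV299 raises the never-positive share and does not when the shares are equal. Neither model puts a rejection rate on symptom resolution, which has no test.

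**The case against.** The strongest defence is that time to negative after peak is naturally a duration among those with something to clear, and the protocol words it that way. Prevention is covered elsewhere: the same participants stay in the primary PCR AUC, culture AUC and peak, and symptom AUC and peak, all with tests. This stands as a reason to keep the positives-only analysis. It does not make that analysis a randomised comparison.

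Other points stand as limits:

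- The rule applies to both arms. A reader might infer that exclusion always shrinks the effect, or removes successes from RV299 only. The text does not support that: placebo participants are dropped too, and with equal shares keeping everyone loses power.
- A reader might also infer that RV299 could appear to clear virus more slowly. With equal clearance in the rest, significantly slower clearance appeared in about 2% of trials, which is chance level. A true reversal needs the further assumption that the remaining RV299 shedders clear more slowly, and the documents give no basis for it.
- The window is all of quarantine, including pre-dose data. Symptom scores come from 3 × 12 + 1 = 37 diary cards (Days 0 to 12), and one mild symptom on any card keeps a participant in. So not every post-dose success is dropped. A participant culture-positive only before dosing stays in, but the peak is defined after first dose and no rule says what their time is.
- Exclusions can partly be inferred from the table shells, which show the number at risk or n against N. The shells do not give the reason for exclusion.
- Counting everyone at the first post-dose assessment cannot be carried over to the from-peak endpoints, where a never-positive participant has no peak, or to time to peak symptoms, where it would assign an arbitrary earliest peak.

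The matching sentence in the qRT-PCR endpoints is harmless in ITT-I, since every member has a PCR positive.

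**Conclusion.** The concern holds in a conditional form. The exclusions select on a post-randomisation outcome that RV299 may change. If RV299 raises the never-culture-positive share, the culture log-rank tests are biased toward no effect. At assumed shares of 20% versus 45% with equal clearance otherwise, rejection is about 5-6% instead of 21-24%; at 10% versus 30%, the exclusion hides all of a 0.8-day restricted mean difference. If the shares are equal there is no such bias, type I error stays near 5%, and the exclusion has somewhat more power (about 31% versus 26% with 20% faster clearance).

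All these sizes rest on assumed shares and clearance times. The symptom-resolution rule has the same selection problem but affects descriptive summaries only, and the primary endpoint is untouched. The point is worth fixing because the shares cannot be known in advance, the log-rank p-values were added to support the study outcome, and the plan provides neither counts nor an analysis of all ITT-I participants for these endpoints.

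**What to change.** Before unblinding, amend SAP 10.7.2.3 and 10.7.2.4:

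1. For the from-first-dose versions of time to culture-negative and time to symptom resolution, add an analysis on all ITT-I participants. Those with no post-dose culture detection, or no post-dose symptoms, have the event at the first scheduled post-dose assessment. Show it beside the positives-only analysis.
2. Report the number and percentage of never-culture-positive and symptom-free participants by arm beside each table.
3. State that the window runs from first IMP dose, so that participants positive only before dosing have a defined result.
4. Keep the from-peak versions restricted to participants with a post-dose peak, and label them so.
5. For time to peak symptoms, do not enter symptom-free participants at their last-assessment time in a mean-and-median table (the layout shared with Table 14.2.3.7.1). Report them separately as having no peak.

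The cost is SAP wording and a few lines of programming, with no new data. The all-participant analysis loses some power if the shares are equal, and its medians are shorter and no longer describe only participants who shed culturable virus or had symptoms.

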10.7.2.4 Clinical Symptom-Related Endpoints

Area under the Curve over Time of Total Clinical Symptoms (TSS-AUC) as Measured from 10 Symptoms within the Graded Symptom Scoring System Collected 3 Times Daily Starting at Initial Administration of IMP up to Planned Discharge from Quarantine

Total symptom scores (from 10 items of the 13-item symptom diary card) will be used to calculate the AUC, from the assessment nearest to the time of the first administration of IMP (can be prior to or after dosing, depending on whether dosed in the morning or evening), i.e. baseline, until Day 12 (Quarantine discharge), for each participant using the trapezoidal rule [1].

Symptoms are assessed 3 times daily for Day 1 to Day 11 (and once for Day 12) and recorded on the symptom diary cards at each assessment. The following types of symptoms are recorded (on a grading scale, 0 to 3 (or 0 to 4 for the Shortness of Breath symptom)):

- Upper Respiratory Tract (URT): runny nose, stuffy nose, sore throat, sneezing, earache.
- Lower Respiratory Tract (LRT): cough, shortness of breath.
- Systemic: headache, malaise, muscle/joint ache/stiffness.
- Not used for analyses: chilliness/feverishness, chest tightness, wheeze.

A total symptom score will be derived for each participant, separately for each assessment (symptom diary card) on each day (Day 0 to Day 12) as follows:

- For each assessment, sum the 10 observed symptom grade values for each symptom diary card to obtain a total symptom score for each symptom diary card. If the participant does not have all 10 observed values on a specific symptom diary card being considered, then total symptom score will not be calculated for that symptom diary card. It is expected that participants will not have missing data.
- The AUC calculation will be based on the available non-missing calculated total symptom scores between the start and end of the defined AUC time. However, for an AUC to be derived, the participant should have at least 1 non-missing calculated total symptom scores at the start of the AUC period (e.g. date of first dose of IMP) and also at the end of the AUC time period

(e.g. Day 12). In addition, the participant should have at least 2 non-missing data recording on each day between the day after the start, and the day before the end, of the defined AUC time period (i.e. at least 2 out of the 3 possible assessments on each Day)). Any missing total symptom score data will be reviewed at the BDRM, for its potential impact on this endpoint, and any decisions to exclude participants as a result of these criteria will be documented in the BDRM minutes.

- As symptoms are scheduled to be taken 3 times daily for Days 0 to 11 (and once on Day 12), in order to calculate the AUC, the actual time that the assessment was collected will be used within the AUC calculation starting from the assessment at the time of the first administration of IMP.

The AUC of the total symptom score will be summarised by treatment group and modelled in the same way as the main analysis of the primary endpoint described in Section 10.7.1, including sensitivity analyses 1 and 2, as described therein.

The total symptom scores and the change from baseline scores will be summarised by timepoint (i.e. day relative to first administration of IMP and assessment) and treatment group. The symptom scores and the visual analogue score (VAS) in millimetres from the 13-item symptom diary card will be listed.

As well as a descriptive statistics summary of total symptom score values, the mean total symptom score values (+/- 1 Standard Error (SE)) will be displayed graphically by day (relative to first dose of IMP) and assessment, and treatment group. In order to calculate the time point that each assessment will be presented against, a relative day and relative assessment will be assigned. The last total symptom score measurement collected at the time of the first dose of IMP will be assigned to be the value at time point 1, while measurements collected on subsequent assessments and days will be assigned to subsequent time points in sequential order (i.e. time point 2, 3 and so on). Time point 1 will be presented against Day 0 assessment 1, while subsequent time points will be presented against Day 0 assessment 2, Day 0 assessment 3, Day 1 assessment 1, and so on. Negative timepoints relative to dosing will also be included and will be presented as Day -1 assessment 1.

[Line graph: y-axis = mean of total symptoms score, x-axis = day relative to dosing (the axis will be negative to include days prior to IMP administration), one line for each treatment group on same plot].

A boxplot will also be presented by day (relative to first dose of IMP) and assessment, plotting the median and mean qRT-PCT values for each treatment group, with the corresponding summary statistics.

[Box plot: y-axis = mean of qRT-PCR (\log_{10} copies/mL), x-axis = day relative to dosing, one box-and-whisker for each day, with each treatment panelled with RV299 at the top and placebo below].

Note: For multiple assessments taken within each day, so as to be able to plot mean values across participants (within a treatment group) by day, the actual collection time point (which may differ across participants) will not be used. Rather all first, second and third assessments will have mean values separately calculated and plotted as three means within each day. These three means will be shown equally spaced along the x-axis within the graph.

Area under the Curve over Time of Total Clinical Symptoms Change from Baseline (TSS-AUC-CFB) as Measured from 10 Symptoms within the Graded Symptom Scoring System Collected 3 Times Daily Starting at Initial Administration of IMP up to Planned Discharge from Quarantine

The change from baseline will be calculated for each assessment following administration of IMP and an AUC calculated using these scores will be analysed in the same manner as described above

(including sensitivity analyses 1 and 2), where the baseline assessment is the assessment nearest to the time of the first administration of IMP (can be prior to or after dosing, depending on whether dosed in the morning or evening).

Peak Symptoms Diary Card Score: Peak Total Clinical Symptoms (TSS) as Measured from 10 Symptoms within the Graded Symptom Scoring System Collected 3 Times Daily Starting from Initial Administration of IMP up to Planned Discharge from Quarantine

Using the scheduled protocol assessments from the assessment at the time of the first dose of IMP to Day 12 (Quarantine discharge), the highest total symptom score (defined as the sum of all 10 individual composite symptoms) will be summarised by treatment group and modelled in the same way as the main analysis of the primary endpoint.

Participants who do not record any symptoms will be assigned a peak of 0.

Peak Daily Symptom Score: Individual Maximum Daily Sum of Symptom Score from Initial Administration of IMP up to Planned Discharge from Quarantine

The highest total symptom score recorded on each day, across the three assessments, for each participant will be summarised descriptively by treatment group and assessment day.

Time to Symptom Resolution as Measured from 10 Symptoms within the Graded Daily Symptom Scoring System Starting at Initial Administration of IMP to 24-hours Symptom Free

Symptom resolution is defined as a participant scoring 0 for the total symptom score for a 24 hour period (e.g a minimum of three consecutive symptom diary cards, each with a score of 0) after their peak symptom score.

The time from the assessment at the time of the first administration of IMP until symptom resolution will be calculated in days as:

Date and time of symptom resolution – Date and time of assessment at IMP administration.

The time to symptom resolution will be summarised by treatment group using descriptive summaries.

If the peak symptom score occurs on more than one day then the first occurrence will be selected. Participants who do not record 24 hours symptom free after their highest total symptom score during the quarantine period will be censored at their last assessment and participants who record no symptoms during quarantine will be excluded from this analysis.

Time to Symptom Resolution as Measured from 10 Symptoms within the Graded Daily Symptom Scoring System Starting at Peak Symptoms after Initial Administration of IMP to 24-hours Symptom Free

The time from the highest total symptom score following administration of IMP until symptom resolution will be calculated in days as:

Date and time of symptom resolution – Date and time of highest total symptom score.

The time to symptom resolution after the peak symptom score will be summarised by treatment group using descriptive summaries.

If the peak symptom score occurs on more than one day then the first occurrence will be selected. Participants who do not record 24 hours symptom free after their highest total symptom score during the quarantine period will be censored at their last assessment and participants who record no symptoms during quarantine will be excluded from this analysis.

Time to Peak as Measured from 10 Symptoms within the Graded Daily Symptom Scoring System Starting from Initial Administration of IMP to the Time of Peak Daily Symptom Score

The time from the assessment at the time of the first dose of IMP (can be prior to or after dosing, depending on whether dosed in the morning or evening) until the highest total symptom score will be calculated in days as:

Date and time of highest total symptom score – Date of and time of assessment at IMP administration.

The time to peak daily symptom score will be summarised by treatment group using descriptive summaries.

If the peak symptom score occurs on more than one day then the first occurrence will be selected. Participants who record no symptoms during quarantine will be censored at their last assessment.

